Intermediate Vision in Patients with Clareon IOLs Compared to Eyhance IOLs

NCT05226884

17 Jan 2022

PROTOCOL TITLE: Intermediate Vision in Patients with Clareon IOLs Compared to Eyhance IOLs

PROTOCOL **BEC001-69901155, NCT05226884**

STUDY TREATMENTS: **Non-interventional (None).**

Principal Investigator: **[name]**

Location: **Berkeley Eye Center, Houston, Texas**

Background:

The recently launched Eyhance IOL is a monofocal designed to slightly extend the depth of focus.

Indications for use “TECNIS Eyhance IOL for the visual correction of aphakia in adult patients in whom a cataractous lens has been removed by extracapsular cataract extraction.”

In two prior Vivity registration studies, the AcrySof IQ monofocal lens was used as the control lens and showed functional intermediate vision (~20/32) via binocular IVA measurement.

Defocus curves also demonstrated a slightly extended depth of focus with the AcrySof IQ and mean visual acuities remained above 0.0 logMAR (20/20 Snellen) between +0.50D~-0.50D defocus.

Clinical data is needed to determine if the Clareon monofocal IOLs can provide similar range of vision as the Eyhance monofocal IOLs.

Clinical Hypothesis:

Patients with bilateral Eyhance IOLs may have improvements in intermediate vision, however, it has previously been reported that bilateral Clareon IOLs also provide improved intermediate vision (see Vivity - Directions For Use).

This study aims to determine the non-inferiority of bilateral Clareon IOLs compared to bilateral Eyhance IOLs at intermediate vision.

Scientific Rationale:

The Eyehance IOL was approved as a Level A Modification of the ZCB00 IOL, thus no clinical data was required for that approval. The inference is that the Eyhance provides an extended range of vision due to the slight modification to the optic design

Study Objectives:

Compare distance and intermediate visual acuities and a defocus curve in patients with bilateral Clareon Monofocal IOLs versus bilateral Eyhance IOLs.

OVERALL STUDY DESIGN

This is a non-interventional prospective, single center, bilateral, non-randomized, open-label, two-arm comparative study of the outcomes for patients following successful, uncomplicated cataract surgery. 155 subjects will be enrolled in each arm of the study, with 310 total subjects. All patients will have had bilateral implantation of an Eyhance IOL (DIB00/DIU***) or Clareon IOL (CNA0T0/CCA0T0) at the time of uncomplicated cataract surgery. These patients will then be assessed at least 3 months post-operatively.

Duration:

12 months or longer to meet required enrollment.

Administration:

Patients with healthy eyes and previously implanted Eyhance IOLs or Clareon IOLs will be offered the opportunity to participate in the study.

Visit Schedule:

All subjects will undergo 1 visit. At the study visit and after informed consent, the subjects' demographic information will be collected, and the subject will have the following testing:

- 1) Manifest refraction (both groups)
- 2) Binocular corrected distance visual acuity (BDVA) at 4m (both groups)
- 3) Distance corrected intermediate visual acuity (DCIVA) at 66 cm (both groups)
- 4) Distance targeted-corrected binocular distance and intermediate visual acuity with +0.25D offset (Clareon group)
- 5) Binocular distance corrected defocus curve from +1.0 D to -3.0 D at 0.5D steps, with 0.25 D steps between -0.50 D and +0.50 D

STUDY POPULATION CHARACTERISTICS:

Condition

Patients with healthy eyes and uncomplicated bilateral implantation of Eyhance IOLs or Clareon IOLs.

Number of Subjects:

Under the assumption that the difference between binocular targeted corrected intermediate visual acuity between the two arms is 0.05 logMAR, thus demonstrating non-inferiority, then 155 patients per arm would be required, for a total of 310 patients. The standard deviation for each measurement is 0.15 logMAR, a power of 80% and Type I error probability of 0.05.

Source: Kohn MA, Senyak J. Sample Size Calculators [website]. UCSF CTSI. 8 August 2021. Available at <https://www.sample-size.net/> [Accessed 28 September 2021]

Inclusion/Exclusion Criteria (all study criteria apply to each study eye unless otherwise indicated):

Inclusions

- 1) Adults, at least 40 years of age having already undergone uncomplicated cataract removal by phacoemulsification with a clear corneal incision in both eyes.
- 2) Implantation of bilateral Clareon IOLs or Eyhance IOLs (DIB00/DIU***).
- 3) Able to comprehend and willing to sign informed consent and complete all required testing procedures
- 4) Best Corrected Distance Visual Acuity (BCDVA) projected to be 0.10 logMAR (Minimum Angle of Resolution) or better
- 5) Clear intraocular media
- 6) Minimum of two weeks post YAG capsulotomy to treat PCO
- 7) Residual refractive astigmatism ≤ 0.75 diopters
- 8) Post op refractive results for the Clareon subjects are from 0.00 to -0.50 SE
- 9) Post op refractive results for the Eyhance subjects are from +0.25 to -0.25 SE

Exclusions

Subjects will not be permitted to enroll in this study if they meet any of the following exclusion criteria:

- 1) Any corneal abnormality, other than regular corneal astigmatism (as determined by pre-operative testing) that in the opinion of the investigator would confound the outcome(s) of the study
- 2) Any complication during cataract surgery (capsular tear, vitrectomy, etc)
- 3) History of or current retinal conditions or predisposition to retinal conditions
- 4) Amblyopia or strabismus in either eye
- 5) History of or current anterior or posterior segment inflammation of any etiology
- 6) Any form of neovascularization on or within the eye
- 7) Glaucoma (uncontrolled or controlled with medication)
- 8) Optic nerve atrophy

- 9) Subjects with diagnosed degenerative eye disorders
- 10) Postoperative CDVA worse than 0.10 logMAR in either eye.
- 11) Subjects who have an acute or chronic disease or illness that would confound the results of this investigation (e.g. immunocompromised, connective tissue disease, clinically significant atopic disease, diabetes, etc)

Outcome Measures:

Primary Endpoints:

1. Non-inferiority of Target-corrected Binocular Intermediate (66 cm) Visual Acuity with Offset: Target-corrected binocular intermediate (66 cm) visual acuity of Clareon monofocal subjects at -0.25 sphere versus Eyhance subjects at plano sphere.
2. Non-inferiority of Distance Corrected Binocular Intermediate Visual Acuity: Distance corrected binocular intermediate visual acuity (measured at 66 cm) of Clareon subjects versus Eyhance subjects with both groups set at plano sphere.
3. Non-inferiority of Best Corrected Distance Visual Acuity: Comparison of Best Corrected Distance Visual Acuity (measured at 4m) of Clareon subjects versus Eyhance subjects.
4. Non-inferiority of Target-corrected Binocular Distance (4 m) Visual Acuity With Offset: Comparison of Best Corrected Distance Visual Acuity (measured at 4m) of Clareon subjects versus Eyhance subjects.
5. Binocular Distance Corrected Defocus Curve: Comparison of the binocular distance corrected defocus curve of Clareon subjects versus Eyhance subjects from +1.0D to -3.00D.

Secondary Endpoints:

1. Post-operative Spherical Equivalent
2. Post-operative Residual Astigmatism

Statistical Analysis

Welch Two Sample t-test for parametric data and Wilcoxon rank-sum test for non-parametric data. Non-inferiority will be defined as within 0.1 LogMAR.

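### Non-randomised arms of already-implanted patients are compared only by unadjusted tests, so an imbalance in age or time since surgery would be read as a lens effect

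*Combined protocol and SAP*

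**What the plan says.** Overall Study Design calls this a "non-interventional prospective, single center, bilateral, non-randomized, open-label, two-arm comparative study". Under Administration, patients who already have Clareon or Eyhance lenses are invited to take part, so arm membership was fixed by earlier clinical choice. No matching or sampling rule is given.

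Two factors that could differ between the arms have only a lower limit. Inclusion 1 admits "Adults, at least 40 years of age", and Overall Study Design has patients "assessed at least 3 months post-operatively". Background says "The recently launched Eyhance IOL is a monofocal designed to slightly extend the depth of focus"; nothing comparable is said about when Clareon became available.

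The Statistical Analysis section consists of two statements: "Welch Two Sample t-test for parametric data and Wilcoxon rank-sum test for non-parametric data" and "Non-inferiority will be defined as within 0.1 LogMAR". Under Visit Schedule, "demographic information will be collected", but no analysis uses it.

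**The concern.** Endpoints 1 to 4 are non-inferiority claims about a lens. In a randomised trial, an unadjusted difference can be attributed to the lens because allocation balances other factors in expectation. Here no allocation mechanism does that. If one arm is older, or was operated on longer ago, and that factor is related to acuity, the Welch or rank-sum comparison passes its effect on to the lens.

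Age is the clearer example. Time since surgery is plausible because a recent launch limits how long ago the Eyhance operations can have been, but neither launch date is given.

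The error can go either way: a false claim that Clareon is non-inferior, or failure to show a true one. A larger sample would not reduce this bias.

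**Working it through.** **Inputs from the plan.** Number of Subjects gives 155 per arm and an assumed difference of 0.05 logMAR, and states: "The standard deviation for each measurement is 0.15 logMAR, a power of 80% and Type I error probability of 0.05". Statistical Analysis gives the margin of 0.10 logMAR.

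**Assumptions, because the plan is silent.**
- One covariate lies d = 0.25 SD apart between arms.
- Its within-arm correlation with acuity is r = 0.1, 0.2, 0.3 or 0.5.
- Non-inferiority is met when the upper limit of a two-sided 95% interval for Clareon minus Eyhance is below 0.10. The plan states neither an interval rule nor sidedness.

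**The plan's own figure.** With margin 0.10, true difference 0.05, one-sided 0.025 and 80% power:

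n = 2 × [0.15 × (1.960 + 0.842)/0.05]² ≈ 141.3, so 142 per arm (112 at one-sided 0.05).

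The stated 155 is reproduced by an equivalence calculation with limit 0.05, true difference 0, alpha 0.05 per side and beta split in two:

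n = 2 × [0.15 × (1.645 + 1.282)/0.05]² = 154.15, so 155.

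The point here does not depend on which basis was used, so I take 155 as given.

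**Standard error and unbiased behaviour.**
- SE = 0.15 × √(2/155) = 0.01704.
- Power at a true difference of 0.05: Φ(0.05/0.01704 − 1.96) = 83.5%.
- False non-inferiority at a true deficit of 0.10: 2.5%.

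**Effect of the imbalance.**
- Bias b = d × r × SD = 0.25 × r × 0.15.
- Bias favouring Clareon: false rate at a true deficit of 0.10 = Φ(b/SE − 1.96).
- Bias against Clareon: power at a true difference of 0.05 = Φ((0.05 − b)/SE − 1.96).

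| r | b (logMAR) | False non-inferiority | Power |
|---|---|---|---|
| none | 0 | 2.5% | 83.5% |
| 0.1 | 0.004 | 4.1% | 77% |
| 0.2 | 0.008 | 6.4% | 70% |
| 0.3 | 0.011 | 9.7% | 62% |
| 0.5 | 0.019 | 19.5% | 45% |

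If the margin is instead compared with the point estimate, the false rate is Φ(b/SE): 50% with no bias, then 59%, 67%, 75% and 86%.

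**Distance endpoints 3 and 4.** Exclusion 10 truncates distance acuity, so an SD of 0.15 fits these less well. At an assumed SD of 0.05 to 0.10, power at a true difference of 0.05 stays at 91% or more even at r = 0.5. For SD 0.10: b = 0.0125, SE = 0.01136, and Φ(0.0375/0.01136 − 1.96) = 91.0%. The false rate at a true deficit of 0.10 does not improve: the SD cancels in b/SE, so under this normal model it is still 19.5% at r = 0.5.

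**What adjustment recovers.** This was simulated with 20,000 runs per setting, a true deficit of 0.10 and bias favouring Clareon. The linear model had arm, the covariate and two unrelated covariates, with HC3 standard errors.
- Unadjusted: 4.0%, 6.2%, 9.3% and 19.4% for the four correlations.
- Adjusted, confounder fully measured: 2.3% to 2.4% throughout.
- Adjusted, measured covariate with reliability 0.5: 3.0%, 4.0%, 5.3% and 8.2%.

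**The case against.** The strongest reply is that the magnitude is hypothetical. In b/SE the SD cancels, leaving 0.25 × r/√(2/155), so the false-claim rates follow from the assumed imbalance and correlation, the sample size and the assumed test. The plan supplies neither imbalance nor correlation. That is true: the omission is certain, while its consequence is a risk that cannot be sized from the documents.

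The scenarios are also the sensitive ones. At a true deficit of 0.12, the false rate at r = 0.5 is 2.1%. At a true difference of zero, the same bias against Clareon leaves power at about 99.8%. The figures matter mainly when the truth lies near the margin or near the plan's own 0.05.

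Shared eligibility helps: one centre, a common CDVA limit, a cylinder limit, clear media, the YAG interval rule and disease exclusions. The media and YAG rules in particular weaken the case for time since surgery, and no text links that factor to acuity. But these rules restrict both arms without equalising age or follow-up, and intermediate acuity, the study's stated aim, has no eligibility limit.

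The choice of covariates is partly judgement, and matching or weighting would also answer the criticism. Adjustment is imperfect, as the reliability-0.5 results show. None of this supports having no adjustment at all.

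**Conclusion.** The concern holds. The arms are non-randomised, the lenses were already in place, and only unadjusted tests are planned, so following the plan would attribute any age or follow-up imbalance related to acuity to the lens. Under the stated assumptions (one covariate 0.25 SD apart, upper-95%-limit rule), a bias of at most 0.019 logMAR, under one-fifth of the margin, is enough to raise a 2.5% error rate to 19.5% or reduce power to 45%. At a correlation of 0.1 the effect is modest. The true size and direction are unknown. This is an inexpensive gap that should be closed; it does not invalidate the study.

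**What to change.** For primary endpoints 1 to 4, make the primary estimate the arm difference from a pre-specified linear model with arm, age at the visit, sex, and months from second-eye surgery to the visit. Declare non-inferiority if the upper limit of its heteroscedasticity-robust two-sided 95% interval is below 0.10 logMAR. Use the same covariates in any between-arm comparison of the defocus curve (endpoint 5).

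- Do not adjust for residual cylinder or spherical equivalent: both arise after implantation and are secondary endpoints.
- Keep the unadjusted Welch result as a sensitivity analysis; the rank-sum result can be kept in the same role. Also report the model without months since surgery, in case that covariate separates the arms strongly. The full model remains the basis for the conclusion.
- Tabulate age, sex and months since surgery by arm.
- State that adjustment does not remove unmeasured confounding or open-label measurement bias.
- Minor: report post-operative spherical equivalent descriptively, because inclusions 8 and 9 set different windows by arm and largely determine it.

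**Cost.** A short change to the analysis section. Age and sex should come from the demographics already collected; the second-eye surgery date must be taken from the surgical record.

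If the covariates predict arm but not acuity, the variance grows by 1/(1 − R²), where R² = (d²/4)/(1 + d²/4):
- d = 0.25: R² = 0.015, and power falls from 83.5% to 82.9%.
- d = 0.67: R² = 0.10, and power falls to 79.5%.
- d = 1.0: R² = 0.20, and power falls to 74.7%.

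In the last two cases a correlation with acuity of only 0.1 gives a bias of 0.010 or 0.015 logMAR, and unadjusted false non-inferiority of 8.5% or 14%. The loss of power is therefore worth accepting.

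### Primary endpoint 4 is headed as distance acuity with the offset but defined by endpoint 3's sentence, so the offset distance comparison has no definition of its own

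*Combined protocol and SAP*

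**What the plan says.** Under Outcome Measures, Primary Endpoints, item 4 reads "Non-inferiority of Target-corrected Binocular Distance (4 m) Visual Acuity With Offset: Comparison of Best Corrected Distance Visual Acuity (measured at 4m"). Its defining sentence, in full, is "Comparison of Best Corrected Distance Visual Acuity (measured at 4m) of Clareon subjects versus Eyhance subjects". Item 3 is defined by that same sentence.

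Item 1, the offset endpoint at 66 cm, states the setting in each arm: "Clareon monofocal subjects at -0.25 sphere versus Eyhance subjects at plano sphere". Item 2 also states it: "of Clareon subjects versus Eyhance subjects with both groups set at plano sphere".

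Two distance tests in the Visit Schedule matter here. Test 2 is "Binocular corrected distance visual acuity (BDVA) at 4m (both groups"). Test 4 is "Distance targeted-corrected binocular distance and intermediate visual acuity with +0.25D offset (Clareon group"). The offset distance reading is therefore taken in Clareon subjects only.

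The Statistical Analysis section gives one margin for non-inferiority, 0.1 logMAR, and two candidate tests (Welch t or Wilcoxon rank-sum). It does not tie either test to a particular endpoint or reading.

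**The concern.** The heading and the definition of a primary endpoint name different measurements. An analyst who works from the definition would compare best corrected acuity in the two arms and report the result under a heading that says the offset was in place. Readers would take it as evidence that the offset leaves distance vision non-inferior. They would see it beside an endpoint 1 result that really was obtained with the offset. Any intermediate gain from the offset would have been tested, and any distance cost would not.

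Endpoint 2, with both arms at plano, is untouched and remains the lens-to-lens comparison at intermediate distance. Endpoint 3 is also sound as written.

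**Working it through.** **1. Comparing the texts.**

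| | Heading | Reading named in the definition | Setting stated for each arm? |
|---|---|---|---|
| Endpoint 1 | Intermediate, offset | Intermediate at 66 cm | Yes: Clareon -0.25, Eyhance plano |
| Endpoint 3 | Best corrected distance | Best corrected distance at 4 m | No |
| Endpoint 4 | Distance, offset | Best corrected distance at 4 m | No |

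An exact comparison of the defining sentences of endpoints 3 and 4 shows no difference. No other section defines the offset distance comparison.

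**2. Whether endpoint 5 fills the gap.** It is described as "Comparison of the binocular distance corrected defocus curve of Clareon subjects versus Eyhance subjects from +1.0D to -3.00D", and visit test 5 adds "with 0.25 D steps between -0.50 D and +0.50 D". The curve therefore has points 0.25 D from zero. But it starts from distance correction and has no stated non-inferiority test, so it bears on the question only indirectly.

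**3. The plan's own sample size.** The Number of Subjects section gives 155 per arm from a difference of 0.05 logMAR in targeted corrected intermediate acuity, SD 0.15, power 80% and type I error 0.05 (sidedness not stated). At 80% power the usual non-inferiority formula (margin 0.1, true difference 0.05) gives 142 per arm at one-sided 0.025 and 112 at one-sided 0.05. An equivalence calculation with limit 0.05, true difference 0 and 0.05 per side does reproduce it: 2 × (0.15 × (1.645 + 1.282) / 0.05)² = 154.15, rounded up to 155. That is a separate matter. N was set on intermediate acuity, and correcting endpoint 4 does not change it.

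**4. How far the two readings of endpoint 4 can diverge.**

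Inputs from the documents: 155 per arm, margin 0.1 logMAR, SD 0.15. Assumptions: that SD applies to distance acuity; the test is one-sided 0.025; true best corrected acuity is equal in the two arms; the offset costs Clareon a true mean of d logMAR at 4 m.

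- SE = 0.15 × √(2/155) = 0.01704
- Probability of passing = Φ((0.1 − d)/SE − 1.960)

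Under the literal definition d does not enter. The true difference is 0, and the probability is Φ(0.1/0.01704 − 1.960), above 99.9%. For the comparison in the heading:

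| Assumed true loss d | SD 0.15, one-sided 0.025 | SD 0.15, one-sided 0.05 (1.645) | SD 0.10, one-sided 0.025 |
|---|---|---|---|
| 0.025 | 99.3% | 99.7% | >99.9% |
| 0.05 | 83.5% | 90.1% | 99.3% |
| 0.075 | 31.1% | 43.0% | 59.5% |
| 0.10 | 2.5% | 5.0% | 2.5% |

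These are normal approximations. With SD 0.15 and one-sided 0.025, the noncentral t gives 83.3% at 0.05 and 30.9% at 0.075. The last row is simply the type I error at the margin.

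**5. Notation.** Visit test 4 writes the offset as +0.25 D; endpoint 1 writes the Clareon setting as -0.25 sphere. A +0.25 D lens over the distance correction could leave the eye at about -0.25 D, so these may be one condition in two conventions. The documents do not say so.

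**The case against.** The strongest reply is that the heading is part of the plan too. It names the quantity, the distance and the hypothesis, and the margin is given elsewhere. Test 2 is the only distance acuity reading scheduled for Eyhance apart from the defocus curve, so the comparator follows almost by elimination. On this view it is a copying slip that a careful analyst would see through. As to intent, that stands: the heading and visit tests 2 and 4 point to an offset comparison. It does not remove the contradiction, because the sentence that should define the endpoint names a different reading and no other section corrects it.

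The power contrast also rests largely on assumption:

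- No document gives a distance loss for the offset. The Background section reports that mean acuity with AcrySof IQ stayed above 20/20 between +0.50 D and -0.50 D of defocus, so the larger assumed losses may be unlikely. But that is a different lens, and no best-focus acuity is given from which to derive a loss.
- The SD of 0.15 comes from the sample size paragraph on intermediate acuity. Exclusion 10 removes subjects with corrected distance acuity worse than 0.10 logMAR in either eye, so the distance SD may be smaller. At SD 0.10 and a loss of 0.05, the two readings barely differ.
- Type I error is stated as 0.05 without a side, so the one-sided 0.05 column is as defensible as the 0.025 column.

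These limits stand. They affect the illustration, not the textual error.

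On notation, inclusion 8 allows Clareon subjects 0.00 to -0.50 SE, centred on -0.25. That fits a single -0.25 condition, so this part is a clarification only.

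**Conclusion.** The concern holds. The definition of primary endpoint 4 duplicates that of endpoint 3 and contradicts its own heading, and no other text defines the offset distance comparison. This conclusion comes from the wording alone and needs no assumption.

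The practical size is unknown because the distance cost of the offset is unknown. If the true loss is 0.025 logMAR or less, both readings would almost certainly pass. If it is 0.05 to 0.075, the comparison in the heading passes with probability 84% down to 31% (SD 0.15, one-sided 0.025), while the literal one passes almost always. Across the alternatives shown, those figures run from 84% to 99% at 0.05 and from 31% to 60% at 0.075. The wording should be corrected before analysis, so that nobody chooses between two readings of a primary endpoint with the results in hand.

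**What to change.** Reword endpoint 4 in the form of endpoint 1. For example: binocular distance visual acuity at 4 m of Clareon subjects with the offset (visit test 4) versus Eyhance subjects at plano sphere (visit test 2), non-inferiority margin 0.1 logMAR.

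Reconcile the +0.25 D of visit test 4 with the -0.25 sphere of endpoint 1, and use one notation in both endpoints and in the schedule.

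It would also help to report any endpoint 1 result alongside endpoint 4, described as Clareon with offset versus Eyhance at plano. Making an endpoint 1 claim formally conditional on endpoint 4 is a further option. Neither is needed to correct the error.

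The cost is one sentence and one notation. Both readings are already scheduled, so no visit, test or sample size changes. The sponsor should expect that the offset distance result may be less favourable than the result without offset. That is a property of the comparison the heading already names, not of the rewording.

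### The 0.1 logMAR non-inferiority margin is not tied to the named tests: no null value, sidedness or confidence limit is given for the four non-inferiority primary endpoints

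*Combined protocol and SAP*

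**What the plan says.** The Clinical Hypothesis section of the combined protocol and SAP makes non-inferiority the aim: "This study aims to determine the non-inferiority of bilateral Clareon IOLs compared to bilateral Eyhance IOLs at intermediate vision". Four of the five primary endpoints are titled as non-inferiority comparisons of Clareon with Eyhance, for example "Non-inferiority of Distance Corrected Binocular Intermediate Visual Acuity".

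The Statistical Analysis section has two sentences. The first names the tests: "Welch Two Sample t-test for parametric data and Wilcoxon rank-sum test for non-parametric data". The second gives the margin: "Non-inferiority will be defined as within 0.1 LogMAR".

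The only error rate is in Number of Subjects: "a power of 80% and Type I error probability of 0.05". It carries no sidedness. The same paragraph bases 155 per arm on a "difference between binocular targeted corrected intermediate visual acuity between the two arms is 0.05 logMAR, thus demonstrating non-inferiority", with an SD of 0.15 logMAR. No section states a null value, a confidence level, or which limit is compared with 0.1.

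**The concern.** A Welch or rank-sum test run in its usual form has a null of no difference, and neither outcome of such a test establishes non-inferiority. The margin sentence is the only success criterion, and an observed difference alone can satisfy it. A rule on the observed difference ignores sampling error, so it cannot hold a Type I error of 0.05 at the margin. An unshifted rank-sum p-value does not refer to a logMAR margin at all.

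Three decision rules use the stated 0.1 and fit the text:

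- an observed difference below 0.1;
- an upper confidence limit below 0.1;
- because *within* can be read in both directions, both confidence limits inside plus or minus 0.1 (equivalence).

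The second and third also depend on whether 0.05 is one- or two-sided. For some results the conclusion on a primary endpoint turns on which rule is used, and in an open-label study that choice should not be left until the data are in.

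**Working it through.** **Inputs.** Margin 0.1 (Statistical Analysis). From Number of Subjects: 155 per arm, SD 0.15, alpha 0.05, power 80%, and a difference of 0.05. The SD is given in the paragraph on targeted intermediate acuity; no SD is given for distance acuity. Deficit means Clareon minus Eyhance in logMAR, where higher is worse.

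**Step 1: reproduce 155.** With SD 0.15 and a distance of 0.05 between the assumed truth and the null, the normal approximation is n = 2 × 0.15² × (sum of z)² / 0.05² = 18 × (sum of z)².

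- Equivalence, limit 0.05, true difference 0, 5% per side, 80% power: 18 × (1.6449 + 1.2816)² = 154.1, so 155. This matches.
- Margin 0.1, true difference 0.05, one-sided 5%, 80% power: 18 × (1.6449 + 0.8416)² = 111.3, so 112.
- The same at one-sided 2.5%: 18 × (1.9600 + 0.8416)² = 141.3, so 142.
- A zero-null test of a 0.05 difference also gives 112 (one-sided) or 142 (two-sided).

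Of the calculations tried, only the first gives 155 at the stated 80% power. Margin 0.1 with true difference 0.05 and one-sided 5% also gives 155, but at 90% power, which the plan does not state. The sample size therefore does not show which decision rule was meant.

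**Step 2: cut-offs.** SE = 0.15 × √(2/155) = 0.01704, with 308 degrees of freedom.

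- One-sided 5%: half-width 1.650 × 0.01704 = 0.0281; the observed deficit must be below 0.1 − 0.0281 = 0.0719.
- One-sided 2.5%: half-width 1.968 × 0.01704 = 0.0335; it must be below 0.0665.
- Point-estimate rule: it must be below 0.10.

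**Step 3: error at and beyond the margin.** The point-estimate rule passes with probability Φ((0.1 − true deficit)/SE). At a true deficit of 0.10 this is Φ(0) = 50% for any sample size.

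| True deficit | Point-estimate rule passes | One-sided 5% limit passes |
|---|---|---|
| 0.10 | 50% | 5% |
| 0.11 | 28% | 1.3% |
| 0.12 | 12% | 0.2% |

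**Step 4: how often the two rules disagree.** This is P(observed < 0.1) minus P(observed < cut-off).

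| True deficit | SD | One-sided 2.5% | One-sided 5% |
|---|---|---|---|
| 0 | 0.15 | under 0.01% | under 0.01% |
| 0.02 | 0.15 | 0.3% | 0.1% |
| 0.05 | 0.15 | 17% | 10% |
| 0.05 | 0.10 (assumed) | 0.7% | 0.3% |

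**Step 5: power of the confidence-limit rule at 155 per arm, margin 0.1.** At a true deficit of 0.05 it is 83% (one-sided 2.5%) or 90% (one-sided 5%). At a true deficit of 0 it exceeds 99.9% for both.

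**The case against.** The strongest reply is that a competent analyst would use a confidence limit anyway, and that the plan's numbers lean that way: 155 comes from a margin-based formula and not from a zero-null test. That is fair as inference. It means nobody should conclude that the sponsor intends a point-estimate rule; that is the worst rule compatible with the text, not necessarily the intended one. But the margin in that formula would be 0.05, not 0.1, and the inference fixes neither the level nor the direction.

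Two limits on size also stand. If the lenses are alike, or differ by 0.02, the rules almost never disagree. And the SD of 0.15 is supported only for targeted intermediate acuity. The eligibility criteria restrict corrected distance acuity to 0.10 logMAR or better, so a mean deficit near 0.10 is hard to reach for best corrected distance acuity, and a smaller SD there would shrink the disagreement.

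A reader might also infer that a non-significant zero-null test would be taken as non-inferiority. The documents do not support this: such a rule never uses 0.1, which the plan makes the definition. Nor do they support saying that the planning difference of 0.05 falls in the disputed range of observed results. That range starts at about 0.067.

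**Conclusion.** The concern holds. The success criterion for four of the five primary endpoints is incomplete, and its literal form passes a lens exactly at the margin half the time against a stated Type I error of 0.05. That 50% follows from symmetry and depends on neither SD nor sample size.

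The practical reach is narrower. On the SD of 0.15, the point-estimate and confidence-limit rules part only for observed deficits of about 0.067 or 0.072 up to 0.10, which becomes common only if Clareon is truly about 0.05 or more worse. These magnitudes assume approximate normality, belong to intermediate acuity, and should not be carried to distance acuity without its own SD.

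The mismatch between the 0.05 behind the sample size and the 0.1 margin is part of the same gap, because the rule cannot be applied until the margin is settled. That 155 came from an equivalence formula is inferred from the match; the plan does not say so.

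**What to change.** Before the data are analysed:

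1. State for each non-inferiority endpoint that Clareon is non-inferior if the upper confidence limit for the mean difference (Clareon minus Eyhance, logMAR, higher is worse) is below the margin.
2. Fix the level: a one-sided 95% limit if the 0.05 is one-sided, or a two-sided 95% interval if it is two-sided.
3. Say that *within* means this one-sided limit. If equivalence is meant, say that both limits must lie within the margin.
4. Use a Welch interval. If a rank-based method is kept, shift it by the margin or use a Hodges-Lehmann interval, and state in advance when it applies.
5. Say whether 0.05 in Number of Subjects is a margin or an assumed true difference, reconcile it with 0.1, and restate the basis of 155 per arm.

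**Cost.** A few sentences and no extra patients. The observed deficit must be below about 0.072 (one-sided 5%) or 0.067 (one-sided 2.5%) instead of 0.10. If the SD were 0.20 (assumed), power at a true deficit of 0.05 would fall to 71% or 59%. If the sponsor decides that the margin is 0.05, the cut-offs become about 0.022 or 0.016, with power of 90% or 83% at a true difference of 0 but 54% or 42% at 0.02.
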